8.1. Efficacy Assessments

Assessment of disease response and progression status in all subjects will be evaluated by the Investigator according to RECIST v 1.1 ([Eisenhauer 2009](#)). Response and progression will be evaluated using imaging scans (see Section 8.1.1), as indicated in the SoA ([Table 1](#) and [Table 3](#)).

8.1.1. Imaging Scans

Computed tomography (CT) or magnetic resonance imaging (MRI) scans may be used, but CT is preferred. The same method must be used throughout the study. Imaging will occur at fixed calendar intervals (i.e., first scan in Stage 1 after 10 weeks [\pm 3 days], then every 9 weeks [\pm 3 days]; scans every 9 weeks [\pm 3 days] in Stage 2) regardless of any changes to visit or cycle schedules. In the case of a CR or PR, a confirmatory scan must be performed per RECIST v1.1 ([Eisenhauer 2009](#)). It is recommended that this scan be performed at 4 (+1) weeks after the initial response.

8.1.2. Investigator Assessment of Response and Progression Status

Assessment of response and progression status will be evaluated by the Investigator at each scheduled disease response assessment as outlined in the SoA ([Table 1](#) and [Table 3](#)). Assessment of response and progression status in all subjects will be evaluated according to RECIST v 1.1

(Eisenhauer 2009) for clinical decision-making and assessment of response. Please see Section 10.1 for detailed descriptions of these response criteria.

8.1.3. Survival Follow-up

Subjects who discontinue both study interventions will participate in the Survival Follow-up which will occur every 3 months (\pm 2 weeks) after the Safety Follow-up Visit for up to 1 year after the last subject is enrolled and dosed. This assessment will be conducted by telephone interview and records review (if available). Information on survival status and initiation of other anticancer therapy (including start date, stop date [if appropriate]; therapy type; and response on treatment) will be collected.

8.2. Safety Assessments

Planned time points for all safety assessments are provided in the SoA (Table 1 and Table 3). Additional visits may be conducted as necessary for any abnormal findings that require medical follow-up.

8.2.1. Physical Examinations and Vital Signs

A full physical examination (PE) will be conducted at Screening. The full PE should include measurements of height and weight, vital signs, general appearance, skin, neck, eyes, ears, nose, throat, lungs, heart, abdomen, back, lymph nodes, extremities, neurological examination, clinical assessment of tumor masses (if evaluable by PE), and review of disease-related constitutional symptoms.

Symptom-directed PEs should include body systems as appropriate and will be conducted at subsequent time points per the SoA (Table 1 and Table 3).

Any pre-existing PE abnormality deemed clinically significant by the Investigator during Screening will be reported as medical history. Any PE abnormality that emerges or has worsened after signing of the ICF and that is assessed as clinically significant by the Investigator will be reported as an AE.

Vital signs will be measured with the subject in a semi-supine position after 5 minutes rest and will include temperature, systolic and diastolic blood pressure, pulse rate, and respiratory rate. Vital sign abnormalities will be assessed for clinical significance.

8.2.2. Electrocardiogram

A standard 12-lead electrocardiogram (ECG), including a description of the cardiac rate, rhythm, interval durations, and an overall impression, will be conducted at Screening, after an approximate 10-minute rest period, per the SoA (Table 1 and Table 3). Corrected QT interval (QTc) will be calculated using the Fridericia correction method (QTcF). The ECG will be performed in triplicate to rule out clinically significant abnormalities. Additional on-treatment ECGs should be performed per the Investigator's discretion as clinically indicated.

8.2.3. Concomitant Medication and Procedures

Concomitant medications and procedures will be assessed and recorded in the CRF during Screening (including those occurring within 30 days before first dose) and at each visit.

8.2.4. Clinical Safety Laboratory Assessments

- See [Table 23](#) for the list of clinical laboratory tests to be performed and the SoA ([Table 1](#) and [Table 3](#)) for the timing and frequency.
- The Investigator must review the laboratory report, document this review, and record any clinically relevant changes occurring during the study in the AE section of the CRF. The laboratory reports must be filed with the source documents. Clinically significant* abnormal laboratory findings are those that are not associated with the underlying disease, unless judged by the Investigator to be more severe than expected for the subjects condition.
- All laboratory tests with values considered clinically significantly abnormal during participation in the study or within 30 days after the last dose of study interventions should be repeated until the values return to normal or baseline or are no longer considered clinically significant by the Investigator or the Medical Monitor.
 - If such values do not return to normal/baseline within a period of time judged reasonable by the Investigator, the etiology should be identified, and the Sponsor notified.
 - All protocol-required laboratory assessments, as defined in [Table 23](#), must be conducted in accordance with the Laboratory Manual and the SoA ([Table 1](#) and [Table 3](#)).
 - If laboratory values from non-protocol specified laboratory assessments performed at the institution's local laboratory require a change in subject management or are considered clinically significant by the Investigator (e.g., SAE or AE or requiring dose modification), then the results must be recorded in the CRF.

*Note: Clinically significant findings are findings that are directly responsible for discontinuation from the study, require treatment or other therapeutic intervention, require further monitoring and/or require further diagnostic evaluation (excluding a repetition of the same procedure to confirm the abnormality). A result outside of the normal range or different from what is expected may be determined to be not clinically significant based on the clinical situation and investigator judgment (i.e., laboratory finding just below or above the normal limit).

8.3. Other Assessments

8.3.1. ECOG Performance Status

ECOG performance status will be assessed at the time points as shown in the SoA ([Table 1](#) and [Table 3](#)). If the ECOG performance status assessed at Screening is performed within 7 days of the first dose, the Screening assessment can be used and does not need to be repeated at C1D1.

8.4. Adverse Event Management

8.4.1. Definition of an Adverse Event

An AE is defined as any untoward medical occurrence in a subject administered a medicinal product that does not necessarily have a causal relationship with this treatment. An AE can, therefore, be any unfavorable and unintended sign (including an abnormal laboratory finding), symptom, or disease temporally associated with the use of a medicinal (investigational) product, whether or not related to the study (investigational) product. This includes an exacerbation of pre-existing conditions or events, concurrent illnesses, drug interaction, or the significant worsening of the indication under investigation. Anticipated fluctuations of pre-existing conditions, including the disease under study that does not represent a clinically significant exacerbation or worsening, need not be considered AEs.

Symptoms of the disease under study/lack of efficacy/disease progression should not be classified as an AE if they are within the normal day-to-day fluctuation or expected progression of the disease.

It is the responsibility of the Investigator to document all AEs that occur during the study. AEs should be reported on the appropriate CRF.

8.4.2. Definition of a Serious Adverse Event

An SAE is any untoward medical occurrence at any dose (including those occurring after the ICF is signed and before dosing) that:

- Results in death
- Is life-threatening (subject is at immediate risk of death from the event as it occurred)
- Requires inpatient hospitalization or prolongation of existing hospitalization
- Results in persistent or significant disability/incapacity
- Results in a congenital anomaly/birth defect

Important medical events that may not result in death, are not immediately life-threatening, or do not require hospitalization may be considered SAEs when, based on appropriate medical judgment, they may jeopardize the subject and may require medical or surgical intervention to prevent one of the outcomes listed in this definition. Examples of such events include allergic bronchospasm requiring intensive treatment in an emergency room or at home, blood dyscrasias or convulsions that do not result in inpatient hospitalization, or the development of drug dependency or drug abuse.

For SAE reporting purposes, hospitalization is defined as inpatient hospital stay. Hospitalizations for elective surgery or other medical procedures that are not related to a treatment-emergent AE (TEAE) are not considered SAEs. Hospitalization, which in the opinion of the Investigator, is unrelated to the study intervention, and due to purely non-medical circumstances (e.g., respite care, lack of a caretaker at home, lack of transportation home) is also not considered to be an SAE. SAEs resulting from PD during the study (including signs and symptoms of progression) if documented by use of appropriate methods, should ONLY be reported as an SAE if the outcome of the PD is fatal during the study or within the safety reporting period (see Section 8.4.3). If the

malignancy has a fatal outcome during the study or within the safety reporting period, then the event should be reported using the term "disease progression" with a CTCAE severity of Grade 5.

Death should not be reported as an SAE. The primary reason for a subject's death should be reported as the SAE, with death reported as the outcome.

8.4.3. Reporting of Adverse Events and Serious Adverse Events

The AE reporting period begins from the time that the subject signs the ICF through and including 30 calendar days after the last study intervention dose. All subjects with treatment-related AEs/SAEs should be observed until resolution or stabilization of the event. Any SAE occurring after the reporting period must be promptly reported if a causal relationship to the study intervention(s) is suspected. If the subject begins a new anticancer therapy, the safety reporting period ends at the time the new treatment is started, however, death must always be reported if it occurs during the AE reporting period irrespective of intervening treatment.

Elective or previously scheduled hospitalizations for pre-existing conditions that have not worsened after initiation of treatment should not be classified as SAEs. For example, an admission for a previously scheduled ventral hernia repair would not be classified as an SAE.

All AEs should be recorded individually unless, in the opinion of the Investigator or designated physician, the AEs constitute components of a recognized condition, disease, or syndrome. In the latter case, the condition, disease, or syndrome should be reported rather than each individual sign or symptom. If a constellation of signs and/or symptoms cannot be medically characterized as a single diagnosis or syndrome at the time of reporting, each individual event should be recorded as an AE or SAE, as appropriate, on the relevant form(s) (SAE Report Form and/or AE CRF). If a diagnosis is subsequently established, it should be reported as follow-up information becomes available. If a diagnosis is determined after the reporting of the constellation of symptoms, the signs/symptoms should be updated to reflect the diagnosis.

Each AE will be evaluated for duration, severity, seriousness, and causal relationship to each study intervention. The action taken with each study intervention and the outcome must also be recorded.

All SAEs, regardless of relationship to each study intervention, must be reported immediately (within 24 hours of awareness of event by Investigator) to the Sponsor and contract research organization pharmacovigilance group. Initial SAE notification should be made by e-mailing or faxing the SAE report form to the e-mail or fax number provided on the SAE report form.

An initial SAE Report may be sent without the Investigator's signature but must be followed by a report signed by the Investigator within 48 hours of becoming aware of the event. Follow-up SAE reports must be submitted by the Investigator as new information becomes available.

The Medical Monitors for this study may be contacted for advice or assistance. Contact details will be provided separately in a study contact list.

8.4.4. Severity of Adverse Events

The severity of the AE will be graded according to the NCI CTCAE, Version 5.0 or higher (see web page https://ctep.cancer.gov/protocolDevelopment/electronic_applications/ctc.htm#ctc_50 for details). Only AEs not listed in the CTCAE should be graded as summarized in [Table 15](#).

Table 15: CTCAE (Version 5.0 or higher) AE Grading

CTCAE Grade	Equivalent To:	Definition
Grade 1	Mild	Discomfort noticed but no disruption of normal daily activity
Grade 2	Moderate	Discomfort sufficient to reduce or affect daily activity; no treatment or medical intervention is indicated, although this could improve the overall well-being or symptoms of the subject
Grade 3	Severe	Inability to work or perform normal daily activity; treatment or medical intervention is indicated to improve the overall well-being or symptoms; delaying the onset of treatment is not putting the survival of the subject at direct risk
Grade 4	Life-threatening/disabling	An immediate threat to life or leading to a permanent mental or physical condition that prevents work or performing normal daily activities; treatment or medical intervention is required to maintain survival
Grade 5	Death	AE resulting in death

Abbreviations: AE: adverse event, CTCAE: Common Terminology Criteria for Adverse Events.

8.4.5. Relationship of Adverse Events to Study Intervention

The Investigator will make a judgment regarding whether or not the AE was related to each study intervention, as outlined below:

- **Definitely related:** This category applies when, after careful medical consideration, there is almost no consideration of other causation.
- **Probably related:** There is a clinically plausible time sequence between onset of the AE and study intervention administration. The AE is unlikely to be caused by a concurrent or underlying illness, other drugs, or procedures. If applicable, the AE follows a clinically consistent resolution pattern upon withdrawal of study intervention.
- **Possibly related:** There is a clinically plausible time sequence between onset of the AE and study intervention administration, but the AE could also have been caused by the concurrent or underlying illness, other drugs, or procedures. Information regarding study intervention withdrawal may be lacking or unclear. “Possible” should be used when study intervention administration is one of several biologically plausible causes of the AE.

- **Unlikely related:** The AE is most likely due to a cause not related to study intervention administration. However, association with the study intervention cannot be completely ruled out.
- **Unrelated:** Another cause of the AE is most plausible, and a clinically plausible temporal sequence is inconsistent with the onset of the AE and study intervention administration and/or a causal relationship is considered biologically implausible.

For the purpose of regulatory reporting requirements, causal relationships of definite, probable, and possible will be considered treatment-related, while unlikely and unrelated will be considered not treatment-related.

8.4.6. Clinical Laboratory Adverse Events

A clinical laboratory AE is any laboratory value that is deemed clinically significant by the Investigator and is accompanied by one of the following:

- requires a medical intervention
- requires a modification or interruption of study intervention
- is accompanied by clinical symptoms

Laboratory abnormalities that do not require medical intervention should not be recorded as AEs and will be captured and reported in the laboratory section of the clinical study report (CSR). If a medical intervention occurs, it should be recorded as a treatment with the abnormal laboratory finding as the AE (e.g., anemia with treatment required and blood transfusion recorded as a procedure, hyperglycemia with treatment required and change in insulin dose recorded on the concomitant medications CRF).

The Investigator should decide, based upon the AE criteria and the clinical condition of the subject, whether a change in a laboratory parameter is clinically significant and therefore represents an AE.

If, at the end of the treatment phase with the study intervention, there are pathological laboratory values that were not present at Baseline, further clinical or laboratory investigations should be performed until the values return to within reference range or until a plausible explanation (i.e., concomitant disease) is found for the pathologic laboratory values.

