Toxicity	Adverse Reaction Grade	Dose Modification and Recommended Management
		
 For confirmed PJP, discontinue duvelisib
Hematologic Adverse Reactions		
Febrile neutropenia	Grade 3-4	
 Interrupt duvelisib until afebrile and resolution of Grade 3 or Grade 4 neutropenia to Grade ≤ 2 (ANC > 1.0 Gi/L) Monitor ANC at least weekly until > 1.0 Gi/L Resume at same dose (first occurrence) or at a reduced dose for subsequent occurrence
Neutropenia	ANC 0.5 to 1.0 Gi/L	
 Maintain duvelisib dose Monitor ANC at least weekly
	ANC less than 0.5 Gi/L	
 Withhold duvelisib. Monitor ANC until > 0.5 Gi/L Resume duvelisib at same dose (first occurrence) or at a reduced dose for subsequent occurrence (see Table 11)
Thrombocytopenia	Platelet count 25 to < 50 Gi/L (Grade 3) with Grade 1 bleeding	
 No change in dose Monitor platelet counts at least weekly
	Platelet count 25 to < 50 Gi/L (Grade 3) with Grade 2 bleeding or Platelet count < 25 Gi/L (Grade 4)	
 Withhold duvelisib Monitor platelet counts until ≥ 25 Gi/L and resolution of bleeding (if applicable) Resume duvelisib at same dose (first occurrence) or resume at a reduced dose for subsequent occurrence (see Table 11)

Toxicity	Adverse Reaction Grade	Dose Modification and Recommended Management
Non-hematologic Adverse Reactions During the Duvelisib Monotherapy Lead-in Only^a		
Non-infectious Diarrhea or colitis	Mild/moderate diarrhea (Grade 1-2, up to 6 stools per day over baseline) and responsive to antidiarrheal agents, OR Asymptomatic (Grade 1) colitis	
 • No change in dose • Initiate supportive therapy with antidiarrheal agents as appropriate • Monitor at least weekly until resolved
	Mild/moderate diarrhea (Grade 1-2, up to 6 stools per day over baseline) and unresponsive to antidiarrheal agents	
 • Withhold duvelisib until resolved • Initiate supportive therapy with enteric acting steroids (e.g., budesonide) • Monitor at least weekly until resolved • Resume at a reduced dose (see Table 11)

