6.7.1. Definition of Dose-limiting Toxicity

Dose-limiting toxicity is defined as an AE that occurs during the initial 4-week period (DLT evaluation period, Cycle 1), is at least possibly related to duvelisib, and fulfills at least 1 of the following criteria:

- Grade 3 or higher febrile neutropenia or Grade ≥ 3 neutropenia with infection or Grade 4 neutropenia lasting more than 7 days
- Grade 4 thrombocytopenia or Grade 3 thrombocytopenia with clinically significant bleeding
- Grade 3 or Grade 4 treatment-related non-hematologic toxicity, except nausea, vomiting, diarrhea and elevations in ALT or AST, which will be considered dose-limiting only if the subject develops:
 - Grade 3 nausea, vomiting, or diarrhea lasting more than 48 hours despite use of appropriate therapy or Grade 4 vomiting or diarrhea
 - Grade 3 elevations in ALT or AST lasting longer than 1 week, Grade 4 elevation in ALT or AST, or any ALT or AST elevations that require permanent discontinuation of study treatment
 - Grade 3 elevations in bilirubin elevation $> 2 \times$ ULN ($> 2 \times$ baseline for subjects with Gilbert's syndrome) lasting longer than 1 week, Grade 4 elevation in bilirubin, or any elevations in bilirubin that require permanent discontinuation of study treatment
 - Alkaline phosphatase (ALP) elevations will be evaluated on a case-by-case basis by the study team in assessing whether there is a DLT
- Grade 3 hypersensitivity reaction lasting longer than 24 hours or Grade 4 hypersensitivity regardless of duration
- A DLT for cardiac dysfunction will include any heart failure that is Grade ≥ 2 NCI CTCAE (Version 5.0 or higher). The AE must be clinically significant and at least possibly related to the study drug in order to be considered a DLT
- Any other toxicity that does not meet the definition of a DLT but requires permanent discontinuation of study treatment or is of concern to the Investigator and Sponsor may be considered to be a DLT

In rare instances, an event may fall within the definition of a DLT, as defined above, but the event may not be considered a DLT (e.g., not clinically meaningful). If this occurs, the Investigator and Sponsor will review the event and supporting data, and the reasons for not considering the event to be a DLT will be clearly documented with supporting rationale. Toxicities will be graded and documented according to the NCI CTCAE (Version 5.0 or higher).

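### Section 8.4.6 both defines a hold-only laboratory abnormality as an AE and says not to record it, which risks under-recording laboratory AEs and missing laboratory DLTs in the 6-subject rule

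*Combined protocol and SAP*

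**What the plan says.** Section 8.4.6 of the protocol starts from a laboratory value that the Investigator judges clinically significant. It becomes an AE if at least one of three things is true: it needs medical intervention, it "requires a modification or interruption of study intervention", or it comes with symptoms. The following paragraph says "Laboratory abnormalities that do not require medical intervention should not be recorded as AEs" and sends such values to the laboratory section of the study report. It continues: "If a medical intervention occurs, it should be recorded as a treatment with the abnormal laboratory finding as the AE", with a transfusion and a change of insulin dose as examples.

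Section 6.7.1 opens: "Dose-limiting toxicity is defined as an AE that occurs during the initial 4-week period". The event must also be at least possibly related to duvelisib. Several of its criteria are laboratory values: "Grade 4 neutropenia lasting more than 7 days", "Grade 4 thrombocytopenia or Grade 3 thrombocytopenia with clinically significant bleeding", and "Grade 3 elevations in ALT or AST lasting longer than 1 week, Grade 4 elevation in ALT or AST".

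Sections 4.1 and 6.7 apply the rule to the first 6 subjects. With at most 1 DLT, enrolment continues at the starting dose. With 2 or more, it stops at that dose. Table 5 lists DLTs and AEs within the Stage 1 primary endpoint.

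**The concern.** The list and the sentence after it give opposite instructions for the same event. A clinically significant value that leads only to a hold satisfies the second condition, yet by the later sentence it is not recorded, because no medical intervention was needed. The same holds for a value accompanied only by symptoms.

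Two things are at stake. The first is completeness of the AE data in both stages, since site staff following the later sentence would leave these events out. The second is the DLT count. A DLT has to be an AE, so an event kept out of AE recording may not reach the DLT assessment. With 6 subjects and a threshold of 2, a single uncounted event turns 2 of 6 into 1 of 6 and changes the decision.

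**Working it through.** **Do the two paragraphs of Section 8.4.6 really conflict?** One could try to read medical intervention as including a study-drug hold. The text does not allow it. The list names the two as separate conditions, and the examples after the sentence are treatments given to the subject. The conflict stands.

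**Does another section settle it?** Section 8.2.4 has clinically relevant laboratory changes entered in the AE section of the CRF. That favours recording, but it adds a second conflict with Section 8.4.6, which is the section specific to laboratory AEs. The last part of Section 8.4.6 tells the Investigator to decide by the AE criteria. That leans towards the three conditions without withdrawing the sentence.

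**Which DLT criteria can be met by a hold-only event?**

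- Neutropenia: for ANC below 0.5, Table 12 says "Withhold duvelisib. Monitor ANC until > 0.5 Gi/L" and lists no treatment. I take this row to be Grade 4; the table does not label it.
- Thrombocytopenia: for platelets below 25 (labelled Grade 4), Table 12 lists hold and monitoring. The Section 6.7.1 criterion needs no bleeding at Grade 4.
- ALT/AST: Table 12 lists hold and monitoring for Grade 3, but only in its block for the monotherapy lead-in. During combination therapy, Table 10 lists corticosteroids for elevations above 3 and up to 5 × ULN, and discontinuation of both drugs above 5 × ULN in subjects without liver metastases. The hold-only example is therefore confined to the lead-in.

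**What happens to the subject?** Table 16 counts a subject as DLT-evaluable with at least 75% of the scheduled Cycle 1 duvelisib doses or with a DLT. Section 5.6 allows replacement below 75%. Cycle 1 has 28 × 2 = 56 doses. With all other doses taken:

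- a 7-day hold leaves 42/56 = 75.0%, still evaluable;
- an 8-day hold leaves 40/56 = 71.4%, not evaluable unless the event counts as a DLT.

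An uncounted event can thus leave the subject in the cohort as a non-DLT, or take the subject out of it altogether.

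**How sensitive is the rule?** The documents give no operating characteristics for the DLT rule, so there is no figure to reproduce. Let p be the true DLT rate and s the share of DLTs that are hold-only laboratory events, all uncounted. Both are assumptions. The chance that enrolment continues is P(X ≤ 1) with X ~ Bin(6, q), that is (1 − q)^6 + 6q(1 − q)^5, where

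- subject kept as a non-DLT: q = p(1 − s);
- subject replaced: q = p(1 − s)/(1 − ps).

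Example: p = 0.20 with s = 0 gives 0.8^6 + 6 × 0.2 × 0.8^5 = 0.262 + 0.393 = 0.655. With s = 0.25 and the subject kept, q = 0.15 and the result is 0.776.

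| p | all counted | kept, s = 0.25 | kept, s = 0.50 | replaced, s = 0.25 | replaced, s = 0.50 |
|---|---|---|---|---|---|
| 0.20 | 0.655 | 0.776 | 0.886 | 0.758 | 0.863 |
| 0.33 | 0.358 | 0.540 | 0.741 | 0.488 | 0.661 |
| 0.40 | 0.233 | 0.420 | 0.655 | 0.351 | 0.534 |
| 0.50 | 0.109 | 0.274 | 0.534 | 0.191 | 0.351 |

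**The case against.** The best reply is that the sentence is an outlier and other provisions would catch the events.

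- Section 6.7.1 names these laboratory grades as DLT criteria in their own right. If an event within the definition is not treated as a DLT, Investigator and Sponsor must review it and document why. It also has a discretionary clause for other toxicities of concern.
- Section 8.2.4 sends clinically relevant changes to the AE section of the CRF.
- All laboratory results go into the CRF (Section 10.3), as do treatment delays and dose reductions (Section 6.4). Grade 3 or 4 laboratory values get their own table (Section 9.4.4). The Sponsor could see the value and the hold together.
- Growth factor and transfusions are permitted under Section 6.6. If given, they are medical interventions and the event is recorded.
- Replacement under Section 5.6 is optional.

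Much of this stands, and it limits the DLT consequence to a risk. It does not remove the contradiction. The documentation duty in Section 6.7.1 starts from an event recognised as falling within a definition that requires an AE. A laboratory table carries no relatedness judgement, which Sections 8.4.3 and 8.4.5 prescribe for AEs.

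A reader might infer more: that laboratory DLTs are in effect removed from the count, with ALT/AST as the leading case. The documents do not support that. The provisions above work against silent loss, and hold-only management of Grade 3 ALT/AST is limited to the lead-in. In combination therapy, elevations that force permanent discontinuation are separately a DLT criterion, the reason for discontinuation is entered in the CRF (Section 7.1), and events leading to discontinuation are listed (Section 9.4.4).

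**Conclusion.** The contradiction is real and lies within Section 8.4.6, with a further conflict against Section 8.2.4. Followed literally, the later sentence under-records laboratory AEs in both stages. For DLTs it creates a risk, not a certainty, that hold-only events such as Grade 4 neutropenia beyond 7 days or Grade 4 thrombocytopenia are missed.

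The tabulated probabilities show how sensitive a 1-versus-2-in-6 rule is; they do not forecast a loss. They rest on an assumed DLT rate of 20% to 50%, an assumed laboratory share of 25% to 50%, and the worst case that every such event goes uncounted. None of these figures is in the documents, and the safeguards make the worst case unlikely to apply in full. The point deserves correction because the affected events belong to the Stage 1 primary endpoint and the remedy is small.

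**What to change.** Reword the sentence in Section 8.4.6 so that a laboratory abnormality is left out of AE recording only when it is not clinically significant or meets none of the three listed conditions. Keep the instruction to report such values in the laboratory section of the study report; deleting the whole sentence would lose it. Add that any laboratory value meeting a Section 6.7.1 criterion is recorded as an AE and assessed for DLT. Bring Section 8.2.4 and the CRF completion guidance into line.

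This concerns recording only and changes no dose or clinical rule. The cost is a short text change and slightly more AE entries.
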